10.10.4. Special Reporting Situations

Safety events of interest on a sponsor study intervention in an interventional study that may require expedited reporting or safety evaluation include, but are not limited to:

- Overdose of a sponsor study intervention
- Suspected abuse/misuse of a sponsor study intervention
- Accidental or occupational exposure to a sponsor study intervention
- Medication error, intercepted medication error, or potential medication error involving a sponsor medicinal product (with or without patient exposure to the sponsor's medicinal product, eg, product name confusion, product label confusion, intercepted prescribing or dispensing errors)
- Exposure to a sponsor study intervention from breastfeeding

Special reporting situations should be recorded in the eCRF. Any special reporting situation that meets the criteria of a serious adverse event should be recorded on the serious adverse event page of the eCRF.

10.10.5. Procedures

All Adverse Events

All AEs, regardless of seriousness, severity, or presumed relationship to study intervention, must be recorded using medical terminology in the source document and the eCRF. Whenever possible, diagnoses should be given when signs and symptoms are due to a common etiology (eg, cough, runny nose, sneezing, sore throat, and head congestion should be reported as "upper respiratory infection"). Investigators must record in the eCRF their opinion concerning the relationship of the adverse event to study therapy. All measures required for AE management must be recorded in the source document and reported according to sponsor instructions.

For all studies with an outpatient phase, including open-label studies, the participant must be provided with a "wallet (study) card" and instructed to carry this card with them for the duration of the study indicating the following:

- Study number
- Statement, in the local language(s), that the participant is participating in a clinical study
- Investigator's name and 24-hour contact telephone number
- Local sponsor's name and 24-hour contact telephone number (for medical personnel only)
- Site number

- Participant number
- Any other information that is required to do an emergency breaking of the blind

Serious Adverse Events

All SAEs that have not resolved by the end of the study, or that have not resolved upon the participant's discontinuation from participation in the study, must be followed until any of the following occurs:

- The event resolves
- The event stabilizes
- The event returns to baseline, if a baseline value/status is available
- The event can be attributed to agents other than the study intervention or to factors unrelated to study conduct
- It becomes unlikely that any additional information can be obtained (participant or health care practitioner refusal to provide additional information, lost to follow-up after demonstration of due diligence with follow-up efforts)

Any event requiring hospitalization (or prolongation of hospitalization) that occurs during participation in the study must be reported as an SAE, except hospitalizations for the following:

- Hospitalization related to biopsy procedures
- Hospitalizations not intended to treat an acute illness or adverse event (eg, social reasons such as pending placement in long-term care facility)
- Surgery or procedure planned before entry into the study (must be documented in the eCRF). Note: Hospitalizations that were planned before the signing of the ICF, and where the underlying condition for which the hospitalization was planned has not worsened, will not be considered SAEs. Any adverse event that results in a prolongation of the originally planned hospitalization is to be reported as a new serious adverse event
- For convenience the investigator may choose to hospitalize the participant for the duration of the intervention period

Disease progression should not be recorded as an AE or SAE term; instead, signs and symptoms of clinical sequelae resulting from disease progression/lack of efficacy will be reported if they fulfill the serious adverse event definition (refer to Adverse Event Definitions and Classifications in Appendix 10 [Section 10.10], Adverse Events, Serious Adverse Events, Product Quality Complaints, and Other Safety Reporting: Definitions and Procedures for Recording, Evaluating, Follow-up, and Reporting). Flares of lupus activity, including LN (see Section 4.1.1), that meet the definition of an SAE will be reported to the sponsor but will not be reported to the Health Authorities during the trial so that blinding may be retained in order to ensure study integrity. Expected progression of disease should not be considered an adverse event (or serious adverse event). However, if determined by the investigator to be more likely related to the study intervention than the underlying disease, the clinical signs or symptoms of progression and the possibility that the study intervention is enhancing disease progression, should be reported per the usual reporting requirements.

Information regarding SAEs will be transmitted to the sponsor using an SAE reporting form, which must be completed and signed by a physician from the study site, and transmitted in a secure manner to the sponsor within 24 hours. The initial and follow-up reports of an SAE should be made by facsimile (fax). Telephone reporting should be the exception and the reporter should be asked to complete the appropriate form(s) first.

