PGA of Disease Activity	X	X		X	X	X	X	X	X	X	X	X	X	X	X	X		
Joint count assessment	X	X		X	X	X	X	X	X	X	X	X	X	X	X	X		
Cutaneous lupus (CLASI)	X	X		X	X	X	X	X	X	X	X	X	X	X	X	X		
Repeat renal biopsy (optional)																X ^h		The pathology report should be submitted to the sponsor. Tissue samples to assess for biomarker analysis should be sought for all renal biopsies for all participants who consent.
Safety Assessments																		
Full physical examination	X																X	A physical examination will be performed at screening and the Week 60/Final safety follow up visit. The head and neck, chest, abdomen, and extremities should be examined, as well as including examinations based on the individual's medical history and manifestations of SLE and LN (edema, skin manifestations, arthritis, etc.).
Targeted physical examination		X		X	X	X	X	X	X	X	X	X	X	X	X	X		Targeted physical examination should also include evaluation of signs or symptoms of infection.
Vital signs	X	X		X	X	X	X	X	X	X	X	X	X	X	X	X	X	
Height	X																	
Weight	X	X							X							X		

Table 1: Schedule of Activities – Main Study (Screening Through Week 60)																		
Phase	Screening ^a	Double-blind Period														Follow-up	Notes	
Week ^b	(≤8 Weeks)	0	D2	4	8	12	16	20	24	28	32	36	40	44	48	52/Final Efficacy Visit ^{c,f}	60 or Final Safety Visit ^{d,g}	
Study Procedure																		
TB evaluation	X	X		X		X		X		X		X		X		X	X	TB evaluation includes an assessment of recent exposure or risk of TB including new or chronic cough, fever, night sweats, unintentional weight loss or recent contact with someone with active TB. If TB is suspected at any time during the study, a chest x ray (consistent with local regulations), and QuantiFERON [®] TB test should be performed. A TST is additionally required if the QuantiFERON [®] TB test is not registered/approved locally or the TST is mandated by local health authorities.
Urine pregnancy test	X	X		X	X	X	X	X	X	X	X	X	X	X	X	X	X	Females of childbearing potential only. A serum pregnancy test may be conducted at screening at the discretion of investigator or if required by local regulations.
Review concomitant therapy	X	X		X	X	X	X	X	X	X	X	X	X	X	X	X	X	
Glucocorticoid tapering		<Weeks 2 to 12>															See Section 6.5.2 and Appendix 7 (Section 10.7) for information on glucocorticoid tapering.	

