		
baseline dose of oral glucocorticoids on study entry is limited to a minimum prednisone equivalent dose of 10 mg/day and maximum 1 mg/kg/day or ≤ 60 mg/day, whichever is lower, which must be tapered starting from Week 2. Additionally, participants are also excluded from the study if they have received oral (PO) or IV cyclophosphamide within 3 months prior to randomization, received a single B-cell targeting agent within 3 months prior to first study intervention administration; or received more than 1 previous B-cell targeting therapy including belimumab within 6 months prior to first administration of the study intervention; or received B-cell depleting therapy (eg, obinutuzumab) within 12 months prior to first administration of the study intervention or have evidence of continued B-cell depletion following such therapy: received anti-tumor necrosis factor (TNF) therapy, other biologic medications, or experimental non-biologic therapeutic agents within the past 90 day, or 5 half-lives prior to screening, whichever is greater . Further detail regarding concomitant medications is provided in Sections 5.1 and 5.1.1.

Risks Due to Study Procedures [if applicable]		
Risks associated with renal biopsy include hematuria, hematoma, and pain.	These risks are well recognized, and the risk of serious complications is rare. ³³	Trained and experienced physicians will be performing the procedure during this study.

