10.10.1. Adverse Event Definitions and Classifications

Adverse Event

An adverse event (AE) is any untoward medical occurrence in a clinical study participant administered a pharmaceutical (investigational or non-investigational) product. An AE does not necessarily have a causal relationship with the intervention. An AE can therefore be any unfavorable and unintended sign (including an abnormal finding), symptom, or disease temporally associated with the use of a medicinal (investigational or non-investigational) product, whether or not related to that medicinal (investigational or non-investigational) product. (Definition per International Conference on Harmonisation [ICH])

This includes any occurrence that is new in onset or aggravated in severity or frequency from the baseline condition, or abnormal results of diagnostic procedures, including laboratory test abnormalities.

Note: The sponsor collects adverse events (AEs) starting with the signing of the ICF (refer to All Adverse Events under Section 8.3.1, Time Period and Frequency for Collecting Adverse Events and Serious Adverse Events Information, for time of last adverse event recording).

For combination products with a device constituent, AEs include those resulting from insufficient or inadequate instructions for use, deployment, implantation, installation, or operation, or any malfunction of the device. It includes any adverse event resulting from use error or from intentional misuse of the investigational device.

Serious Adverse Event

A serious adverse event (SAE) based on ICH and EU Guidelines on Pharmacovigilance for Medicinal Products for Human Use is any untoward medical occurrence that at any dose:

- Results in death
- Is life-threatening
(The participant was at risk of death at the time of the event. It does not refer to an event that hypothetically might have caused death if it were more severe.)
- Requires inpatient hospitalization or prolongation of existing hospitalization
- Results in persistent or significant disability/incapacity
- Is a congenital anomaly/birth defect
- Is a suspected transmission of any infectious agent via a medicinal product
- Is Medically Important*

*Medical and scientific judgment should be exercised in deciding whether expedited reporting is also appropriate in other situations, such as important medical events that may not be immediately

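### The biopsy exception in Protocol 10.10.5 has no limit and, read literally, takes an admission for a biopsy complication out of SAE reporting

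*Protocol*

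**What the plan says.** The Serious Adverse Events part of Protocol 10.10.5 says that an event requiring hospitalization, or prolonging it, "must be reported as an SAE, except hospitalizations for the following". Four exceptions follow:

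- The first reads, in full, "Hospitalization related to biopsy procedures".
- The second is "Hospitalizations not intended to treat an acute illness or adverse event", with a social admission as its example.
- The third concerns surgery or procedures planned before study entry. Its note on stays planned before consent ends: "Any adverse event that results in a prolongation of the originally planned hospitalization is to be reported as a new serious adverse event".
- The fourth is admission for the investigator's convenience.

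Protocol 10.10.1 lists among the criteria for an SAE an event that "Requires inpatient hospitalization or prolongation of existing hospitalization", with no biopsy exception. Protocol 8.3.1 requires every SAE to reach the sponsor within 24 hours and starts AE collection at signed consent, again with no biopsy exception.

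Biopsy is a study procedure. Table 1 of the Schedule of Activities requires a renal biopsy in screening if none was done in the preceding 6 months, and places an optional repeat biopsy at the Week 52/Final Efficacy Visit. Protocol 2.3.1 says: "Risks associated with renal biopsy include hematuria, hematoma, and pain". It adds that serious complications are rare.

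**The concern.** The first exception turns on whether an admission is related to a biopsy. It does not ask whether the stay was planned or whether the participant was being treated for harm. An admission for a hematoma the day after a biopsy is related to the biopsy in the ordinary sense of the word. A site could therefore follow 10.10.5 to the letter and not send an SAE form, although 10.10.1 and 8.3.1 require one.

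At stake is prompt and correct classification of harm from a procedure that the protocol itself requires or offers. Section 2.3.1 contains no reporting rule; its relevance is only that it shows such complications to be foreseeable.

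**Working it through.** No arithmetic applies. The check takes one test case through each section.

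**Test case.** After signing consent, a participant has a renal biopsy, develops a hematoma and is admitted for it, or is kept in longer because of it. The event is not life-threatening, leaves no disability, and is not judged medically important.

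1. **10.10.1.** The hospitalization criterion is met, so the event is an SAE.
2. **8.3.1.** The event falls in the collection period and must be reported within 24 hours.
3. **10.10.5, general rule.** Same answer: an SAE.
4. **10.10.5, first exception, read literally.** The admission is related to a biopsy procedure, so it is exempt. This contradicts steps 1 to 3.
5. **Does anything nearby limit the exception?** The restriction to stays that do not treat an adverse event belongs to the second bullet only. The note in the third bullet concerns stays planned before consent and covers prolongation only. A biopsy done for the protocol takes place after consent, and a new admission for bleeding is not a prolongation. Neither limit reaches the first bullet.
6. **What survives the exception?** Section 10.10.5 still requires every AE to be entered in the source document and eCRF whatever its seriousness, and the AE row of Table 1 asks for hospital stays between visits to be documented. The other criteria in 10.10.1 are untouched: death, threat to life, disability, and "Is Medically Important". Protocol 9.5 has the sponsor's physician review blinded safety data regularly and the DMC review unblinded safety data.
7. **What is lost?** The serious classification, the 24-hour report, and the notification of SAEs to DMC members as they arise (SAP 5.9.2).
8. **Which tables could change?** Protocol 9.4.6 and SAP 5.7.2 count events at or after the first administration as treatment-emergent, and the SAE tables are limited to these. A complication arising from the screening biopsy before the first dose stays outside those tables under any wording. A complication of the repeat biopsy could enter them.
9. **Is the repeat biopsy still possible?** Yes. Under footnote c of Table 1, participants still on study intervention when sites are notified of termination have a final efficacy visit about 4 weeks after their last dose, and the repeat biopsy sits in that column. The documents give no count.

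The bullet is also not limited to renal biopsy. Protocol 10.11.2.1 contemplates liver biopsy after a liver event. That liver event itself already calls for an SAE form, but a complication of the biopsy would be a separate event.

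**The case against.** The best case for the present text is that it was meant only for stays to perform a biopsy. The lead-in exempts hospitalizations *for* the listed items, and an admission to treat a hematoma is for the hematoma. The other three bullets concern elective, planned or logistical stays. On that reading there is no contradiction, only loose wording.

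This stands in part: the narrow reading is available and may well be what was intended. But the operative words are *related to*, nothing in the section rules out the wide reading, and sites apply what is written.

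A reader might infer that the biopsy bullet *must* add complication admissions, because the second bullet already covers planned stays. The documents do not support that step. The exceptions overlap: the convenience bullet also falls within the second. The biopsy bullet also has an ordinary use, for a repeat biopsy arranged after study entry, which the third bullet does not reach. Redundancy therefore proves nothing about intent.

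It is also fair to say that several safeguards remain. Many bleeds that need an intervention would qualify as medically important, and the AE record would still show the event. This narrows the consequence. It does not remove the conflict between 10.10.5 and the other two sections.

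**Conclusion.** The concern holds as an internal contradiction in the SAE rules. Under the literal wording of 10.10.5, a biopsy complication that is serious only through admission or a prolonged stay need not be reported as an SAE; under 10.10.1 and 8.3.1 it must be.

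The size is limited and cannot be put in numbers, because the documents give neither the number of biopsies done or to come nor a complication rate. The effect also depends on at least one site reading the bullet literally.

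Three stronger conclusions might be inferred, and none is supported:

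- That these events vanish from the sponsor's and DMC's view. They must still be recorded as AEs, and safety data are reviewed.
- That 2.3.1 contradicts 10.10.5. It sets no reporting rule.
- That SAE tables are distorted generally. Only biopsies after the first dose can matter there.

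The wording should nevertheless be corrected. It concerns harm from a study procedure, the repeat biopsy can still take place, and a single database lock at the end of study leaves time to check.

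**What to change.** Reconcile 10.10.5 with 10.10.1 and 8.3.1:

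- Limit the first exception to hospitalization or observation for the biopsy procedure itself, without complication.
- State that admission or a prolonged stay because of a biopsy complication is reported as an SAE.
- Before the database lock, ask sites to check all biopsy-related admissions since consent and to reclassify where needed.

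The vehicle depends on intent. Protocol 10.9.1 allows a protocol clarification communication only where study conduct does not change, and not as a substitute for an amendment. If only planned, uncomplicated stays were ever meant, a clarification is enough. If the bullet was meant, or has been applied, to exempt complications, narrowing it changes reporting and needs an amendment with ethics committee approval.

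The cost is the text change and one site query, with the approval step if an amendment is needed. The downside is possibly a few more SAE reports.

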10.10.6. Product Quality Complaint Handling

Definition

A product quality complaint (PQC) is defined as any suspicion of a product defect related to manufacturing, labeling, or packaging, ie, any dissatisfaction relative to the identity, quality, durability, reliability, or performance of a distributed product, including its labeling, drug delivery system, or package integrity. A PQC may have an impact on the safety and efficacy of the product. In addition, it includes any technical complaints, defined as any complaint that indicates a potential quality issue during manufacturing, packaging, release testing, stability monitoring, dose preparation, storage, or distribution of the product or the drug delivery system.

This definition includes any PQC related to a device constituent in a combination product, including those used in the administration of the study intervention or the comparator. A device deficiency is an inadequacy of a device with respect to its identity, quality, durability, reliability, safety, or performance. Device deficiencies include malfunctions, use errors, and inadequate labeling.

Procedures

All initial PQCs must be reported to the sponsor by the study-site personnel within 24 hours after being made aware of the event.

A sample of the suspected product should be maintained under the correct storage conditions until a shipment request is received from the sponsor.

10.10.7. Contacting Sponsor Regarding Safety, Including Product Quality

[figure not shown]
The names (and corresponding telephone numbers) of the individuals who should be contacted regarding safety issues, PQC, or questions regarding the study are listed in the Contact Information page(s), which will be provided as a separate document.

10.11. Appendix 11: Liver Safety: Suggested Actions and Follow-up Assessments

10.11.1. Stopping Algorithm

Study intervention will be discontinued for a participant if liver chemistry stopping criteria are met.

Phase 2 Liver Chemistry Stopping Criteria and Increased Monitoring Algorithm (no preexisting liver disease)

10.11.2. Follow-up Assessments**10.11.2.1. Phase 2 Liver Chemistry Stopping Criteria and Follow-up Assessments**

Phase 2 liver chemistry stopping criteria are designed to assure participant safety and to evaluate liver event etiology.

Liver Chemistry Stopping Criteria	
ALT/AST--absolute	ALT or AST- $\geq 5 \times \text{ULN}$
ALT/AST-Increase	
If cannot monitor: ALT or AST- $\geq 3 \times \text{ULN}$ and cannot be monitored weekly for 4 weeks
 
Or if able to monitor: ALT or AST- $\geq 3 \times \text{ULN}$ persists for ≥ 4 weeks

Total bilirubin^{1, 2}	ALT or AST- $\geq 3 \times \text{ULN}$ and total bilirubin $\geq 2 \times \text{ULN}$ (or at least a doubling of direct bilirubin in known Gilbert's syndrome)
INR²	ALT or AST- $\geq 3 \times \text{ULN}$ and international normalized ratio (INR) > 1.5 , if INR measured
Symptomatic³	ALT or AST- $\geq 3 \times \text{ULN}$ associated with symptoms (new or worsening) believed to be related to liver injury or hypersensitivity
Suggested Actions, Monitoring and Follow-up Assessments	
Actions	Follow-up Assessments

 • Immediately stop study intervention • Report the event to the sponsor within 24 hours • Complete an SAE form • Perform follow-up assessments as described in the Follow Up Assessment column • Monitor the participant until liver chemistry test abnormalities resolve, stabilize, or return to baseline (see MONITORING) 
MONITORING: If ALP $< 2 \times \text{ULN}$, ALT or AST- $\geq 3 \times \text{ULN}$ AND total bilirubin $\geq 2 \times \text{ULN}$ (or at least a doubling of direct bilirubin in known Gilbert's syndrome) or INR > 1.5 (if measured):
 
 • Repeat liver chemistry tests (include ALT, aspartate transaminase [AST], alkaline phosphatase, total and direct bilirubin and INR) and perform liver event follow-up assessments within 24 hours • Monitor participant twice weekly until liver chemistry test abnormalities resolve, stabilize, or return to baseline 	
 • Viral hepatitis serology⁴ • Obtain INR and recheck with each liver chemistry assessment until the transaminases values show downward trend • Obtain blood sample for pharmacokinetic (PK) analysis after the most recent dose⁵ • Obtain serum creatine phosphokinase (CPK), lactate dehydrogenase (LDH), gamma-glutamyltransferase [GGT], glutamate dehydrogenase [GLDH], and serum albumin • Fractionate bilirubin • Obtain complete blood count with differential to assess eosinophilia • Record the appearance or worsening of clinical symptoms of liver injury, or hypersensitivity, on the CRF as per CRF completion guidelines • Record use of concomitant medications (including


 • A specialist or hepatology consultation is recommended 
If ALT or AST- $\geq 3 \times \text{ULN}$ AND total bilirubin $< 2 \times \text{ULN}$ and INR ≤ 1.5:
 
 • Repeat liver chemistry tests (include ALT, AST, alkaline phosphatase, total and direct bilirubin and INR) and perform liver chemistry follow-up assessments within 24 to 72 hours • Monitor participant weekly until liver chemistry abnormalities resolve, stabilize, or return to baseline 
RESTART/RECHALLENGE
 
 • If liver event causality is determined to be “not related”, restart may be permitted upon written approval of the sponsor. See restart guidelines 	
acetaminophen, herbal remedies, recreational drugs and other over-the-counter medications)
 
 • Record alcohol use on the CRF as per CRF completion guidelines 
If ALT or AST- $\geq 3 \times \text{ULN}$ AND total bilirubin $\geq 2 \times \text{ULN}$ or INR > 1.5 (if measured) obtain the following in addition to the assessments listed above:
 
 • Anti-nuclear antibody, anti-smooth muscle antibody, Type 1 anti-liver kidney microsomal antibodies, and quantitative total immunoglobulin G (IgG) or gamma globulins • Serum acetaminophen adduct assay, when available, to assess potential acetaminophen contribution to liver injury in participants with definite or likely acetaminophen use in the preceding week • Liver imaging (ultrasound, magnetic resonance, or computerized tomography) and/or liver biopsy to evaluate liver disease; complete CRF as per CRF completion guidelines • Liver biopsy may be considered and discussed with local specialist if available: 
 In participants when serology raises the possibility of autoimmune hepatitis (AIH) In participants when suspected DILI progresses or fails to resolve on withdrawal of study intervention In participants with acute or chronic atypical presentation • If liver biopsy conducted complete CRF as per CRF completion guidelines
--	---

1. Serum bilirubin fractionation should be performed if testing is available. If serum bilirubin fractionation is not immediately available, discontinue study intervention if ALT **or** AST $\geq 3 \times \text{ULN}$ **and** total bilirubin $\geq 2 \times \text{ULN}$. Additionally, if serum bilirubin fractionation testing is unavailable, **record the absence/presence of detectable urinary bilirubin on dipstick** which is indicative of direct bilirubin elevations suggesting liver injury.
2. All events of ALT **or** AST- $\geq 3 \times \text{ULN}$ **and** total bilirubin $\geq 2 \times \text{ULN}$ (or at least a doubling of direct bilirubin in known Gilbert’s syndrome), ALT **or** AST- $\geq 3 \times \text{ULN}$ **and** INR > 1.5 (if measured) may indicate severe liver injury (**possible ‘Hy’s Law’**) **and must be reported to sponsor in an expedited manner as an SAE**. The INR stated threshold value will not apply to participants receiving anticoagulants.

3. New or worsening symptoms believed to be related to liver injury (such as fatigue, nausea, vomiting, right upper quadrant pain or tenderness, or jaundice) or hypersensitivity (such as fever, rash or eosinophilia).
4. Includes: hepatitis A immunoglobulin M (IgM) antibody; HBsAg and HBcAB; hepatitis C RNA; cytomegalovirus IgM antibody; Epstein-Barr viral capsid antigen IgM antibody (or if unavailable, heterophile antibody or monospot testing); and hepatitis E IgM antibody.
5. PK sample may not be required for participants known to be receiving placebo or non-comparator interventions. Record the date/time of the PK blood sample draw and the date/time of the last dose of study intervention prior to the blood sample draw on the CRF. If the date or time of the last dose is unclear, provide the participant's best approximation. If the date/time of the last dose cannot be approximated, do not obtain a PK sample. Instructions for sample handling and shipping are in the laboratory manual.

